### **Randomised tablet formulation continued supply expansion phase (Group 8)**

The Primary objective is:

[figure not shown]
- To determine the safety and tolerability profile of selected tablet dose schedules of the melt-extrusion (tablet) formulation.

The Secondary objectives are:

- To determine the single dose and steady state exposures achieved with the selected tablet dose schedules of AZD2281 melt-extrusion (tablet) formulation.
- To obtain a preliminary assessment of the effect of food on the exposure to AZD2281 following dosing of the melt-extrusion (tablet) formulation.
- To describe the efficacy data observed in patients treated with the melt-extrusion (tablet) formulation.

Exploratory Objectives:

- To perform exploratory biomarker analysis and to correlate biomarker data with disease progression/response to therapy from optional archival tumour samples.

- 
- To further characterise the nature and profile of common low grade AEs associated with AZD2281 (nausea, vomiting and fatigue) to maximise understanding of these adverse events and inform future data collection and CRF design.

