#### **4.1.2.5 Randomised comparison between different tablet dose schedules**

Following the completion of Group 6, approximately 60 confirmed gBRCA1/2 ovarian cancer patients will be randomised to Group 8 to assess the multiple dose safety profile of the Melt-extrusion (tablet) formulation in differing dose schedules. The patients will be randomised on a 1:1:1:1 ratio to the following dosing schedules:

- Schedule A: 200mg tds tablet continuous dosing
- Schedule B: 250mg tds tablet 2 weeks on study drug, 1 week off study drug
- Schedule C: 400mg bid tablet 1 week on study drug, 1 week off study drug
- Schedule D: 400mg od tablet continuous dosing

All patients may receive treatment for as long as they remain free from intolerable toxicity and, in the Investigator's opinion, are receiving some clinical benefit from AZD2281 and do not meet any other discontinuation criteria.

[figure not shown]
Patients who experience NCI-CTCAE of grade 3 or 4 toxicity and meet the criteria outlined in Section 5.5.1 for AZD2281 will have their study medication stopped. The safety follow-up should be continued as outlined in the study schedule.

Once patients receiving AZD2281 have been discontinued from study medication, other treatment options will be at the discretion of the Investigator.

[figure not shown]

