- i For the additional patients recruited to Group 6, 7 and 8, the imaging modalities used for RECIST assessment will be CT or MRI scans of chest, abdomen and pelvis for breast cancer and abdomen and pelvis for ovarian cancer with other regions as clinically indicated for the assessment of disease. An historical scan meeting the RECIST criteria as defined in Appendix F can be used for baseline assessment, but this must be performed no more than 28 days before the first dose of study medication.
- j After the follow up visit at the end of the 6th cycle of treatment (Visit 13), this visit should be repeated at least every 8 weeks until either the patient discontinues study treatment or the study is completed (clinical database is closed) (see Section 10.5).
- k Pre-menopausal women of child-bearing potential must have a negative urine or serum pregnancy test within 28 days prior to Day 1 and Day 1 (prior to treatment). In the event of suspected pregnancy during the study, the test should be repeated and, if positive, the patient discontinued from study treatment immediately.
- l Blood samples for CA-125 analysis should be taken prior to the morning dose of study medication for ovarian cancer patients only.
- m Haematology and clinical chemistry will also be performed on Day 43 and 71 for Group 3, 4 and 5 patients.
- n For the additional patients recruited to Group 6, 7 and 8, archival tumour samples will be requested. This is not mandatory and will not affect the enrolment of the patients into the study if not available. The sample can be collected at any time during the study.
- o For all patients enrolled into Group 8 blood samples will be collected at the following timepoints:

OD schedule

Day 1: pre-dose, 0.25, 0.5, 1, 1.5, 2, 3, 4, 6, 8, 10, 12, 24 hours after dosing

Day 8: pre-dose, 0.25, 0.5, 1, 1.5, 2, 3, 4, 6, 8, 10, 12, 24 hours after dosing

Day 57: pre-dose, 0 – 0.5, 0.5 – 1.5, 1.5 – 3, 3 – 6, 6 – 8, 8 – 12 hours after dosing

BD schedule:

Day 1: pre-dose, 0.25, 0.5, 1, 1.5, 2, 3, 4, 6, 8, 10, 12 hours after dosing

Day 8: pre-dose, 0 – 0.5, 0.5 – 1.5, 1.5 – 3, 3 – 6, 6 – 8, 8 – 12 hours after dosing

Day 57: pre-dose, 0 – 0.5, 0.5 – 1.5, 1.5 – 3, 3 – 6, 6 – 8, 8 – 12 hours after dosing

TDS schedule:

Day 1: pre-dose, 0.25, 0.5, 1, 1.5, 2, 3, 4, 6, 8 hours after dosing

Day 8: pre-dose, 0 – 0.5, 0.5 – 1.5, 1.5 – 3, 3 – 6, 6 – 8 hours after dosing

Day 57: pre-dose, 0 – 0.5, 0.5 – 1.5, 1.5 – 3, 3 – 6, 6 – 8 hours after dosing

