- Tumour marker CA-125 will be assessed locally from blood samples taken at screening, visit 2 and every 8 weeks thereafter (applicable to ovarian cancer patients only). For Group 8 patients this assessment should stop at the end of cycle 5.
  - Tumour assessments (CT or MRI scans of chest, abdomen and pelvis for breast cancer and abdomen and pelvis for ovarian cancer with other regions as clinically indicated for the assessment of disease). For Group 8 patients this assessment should stop at the end of cycle 5.

[figure not shown]
Additional assessments for Groups 2, 3, 4, 5, 5.1.....6 and 7 include:

- Blood sampling for determination of AZD2281 plasma concentration at the following timepoints: Pre-dose, 0.25, 0.5, 1, 1.5, 2, 3, 4, 6, 8, 10, 12 hours after dosing at:
  - Group 2 – Day 8 and Day 15
  - Group 3 to 7 – Day 1
- Blood sampling for determination of AZD2281 plasma concentration at the following timepoints: Pre-dose and 1 hour after morning dose
  - Groups 3 to 7 – Day 8 and Day 15
- Blood sampling for determination of AZD2281 plasma concentration at the following timepoints: immediately prior to the first dose of the day and post the first dose of the day between 0 - 0.5 hours, 0.5 to 1.5 hours, 1.5 - 3 hours, 3 - 6 hours, 6 - 8 hours and 8 - 12 hours
  - Group 3 to 5 – Day 29
  - Group 6 and 7 – Day 29 and Day 57

Additional assessments for Group 8 include:

- Blood sampling for determination of AZD2281 plasma concentration for each dose schedule at the following timepoints:  
od schedule:
  - Day 1: pre-dose, 0.25, 0.5, 1, 1.5, 2, 3, 4, 6, 8, 10, 12, 24 hours after dosing
  - Day 8: pre-dose, 0.25, 0.5, 1, 1.5, 2, 3, 4, 6, 8, 10, 12, 24 hours after dosing
  - Day 57: pre-dose, 0 - 0.5, 0.5 - 1.5, 1.5 - 3, 3 - 6, 6 - 8, 8 - 12 hours after dosing

bd schedule:

- Day 1: pre-dose, 0.25, 0.5, 1, 1.5, 2, 3, 4, 6, 8, 10, 12 hours after dosing
- Day 8: pre-dose, 0 – 0.5, 0.5 – 1.5, 1.5 – 3, 3 – 6, 6 – 8, 8 – 12 hours after dosing
- Day 57: pre-dose, 0 – 0.5, 0.5 – 1.5, 1.5 – 3, 3 – 6, 6 – 8, 8 – 12 hours after dosing

tds schedule:

- Day 1: pre-dose, 0.25, 0.5, 1, 1.5, 2, 3, 4, 6, 8 hours after dosing
- Day 8: pre-dose, 0 – 0.5, 0.5 – 1.5, 1.5 – 3, 3 – 6, 6 – 8 hours after dosing
- Day 57: pre-dose, 0 – 0.5, 0.5 – 1.5, 1.5 – 3, 3 – 6, 6 – 8 hours after dosing

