For the patients in Group 1 of the Continued supply phase, non-linear mixed effects modelling will be used for the evaluation of the AZD2281 steady state plasma concentration-time data to determine the maximum steady state drug concentration in the plasma during the dosing interval ( $C_{ss,max}$ ), the minimum steady state drug concentration in plasma ( $C_{ss,min}$ ) and the area under the plasma concentration-time curve during the dosing interval at steady state (AUCss). For those patients in Group 2, non-compartmental methods will be used for the evaluation of the steady state plasma concentration-time data to determine  $C_{ss,max}$ ,  $C_{ss,min}$  and AUCss for both the Melt Extrusion (tablet) formulation and the Gelucire® 44/14 (capsule) formulation. For the patients in Groups 3 to 8 non compartmental methods will be used to determine single dose  $C_{max}$ ,  $C_{min}$  and  $AUC_{0-8}/AUC_{0-12} / AUC_{0-24}$  and non-linear mixed effects modelling will be used to determine steady state  $C_{ss,max}$ ,  $C_{ss,min}$ , and AUCss.

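### Group 8 PK sampling days are set by dosing frequency alone and do not fit the on/off calendars of the two intermittent schedules

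*Protocol*

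**What the plan says.** Protocol Section 4.1.2.5 defines the two intermittent arms as "Schedule B: 250mg tds tablet 2 weeks on study drug, 1 week off study drug" and "Schedule C: 400mg bid tablet 1 week on study drug, 1 week off study drug". Schedules A and D are continuous. The synopsis gives Group 8 this secondary objective: "To determine the single dose and steady state exposures achieved with the selected tablet dose schedules of AZD2281".

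Table 7 footnote o sets the sampling days under three labels: od, bd and tds. Each label has Days 1, 8 and 57, and every sample is timed before or after a dose. Schedule C is the only bd arm, and its second profile is "Day 8: pre-dose, 0 – 0.5, 0.5 – 1.5, 1.5 – 3, 3 – 6, 6 – 8, 8 – 12 hours after dosing". Schedules A (continuous) and B (intermittent) share the tds list, which ends with "Day 57: pre-dose, 0 – 0.5, 0.5 – 1.5, 1.5 – 3, 3 – 6, 6 – 8 hours after dosing". Section 7.2.2.3 repeats the same lists. Table 7 allows 2 days either side of Day 57 and prints no window for Day 8.

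For Groups 3 to 8, Section 12.1.1 states that "non-linear mixed effects modelling will be used to determine steady state" parameters. It does not say which days supply them.

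**The concern.** The sampling days follow the number of doses per day and take no account of the weeks off. A site that follows the nominal days in an intermittent arm can arrive at a visit with no dose to sample around, or at a first dose after a drug-free week. It must then skip the profile, give a dose in an off week, or improvise.

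The protocol does give PK-day dosing instructions elsewhere: Section 6.2.3.2 tells the od arm how to dose on Days 1 and 8. It gives no such instruction for Schedules B and C. A missed profile cannot be recovered later. A single-dose profile taken for a steady-state one would understate exposure in the arm concerned.

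**Working it through.** **Which days are Group 8 PK days.** Section 8.1 gives a maximum of 33 samples and 165 mL. Counting footnote o:

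- od: 13 + 13 + 7 = 33
- bd: 12 + 7 + 7 = 26
- tds: 10 + 6 + 6 = 22

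At 4 mL plus 1 mL cannula overage, 33 × 5 = 165 mL, so the stated figure is reproduced. Footnote f places a Day 29 profile in Groups 3 onwards. Adding its 7 samples would bring the od arm to 40, so Day 29 is not a Group 8 PK day. It would not help Schedule C in any case: 29 = 2 × 14 + 1, again a first on-day.

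**Calendar.** With Day 1 as the first on-day, the position in the repeat is ((day − 1) mod (on + off)) + 1. The repeat is 14 + 7 = 21 days for Schedule B and 7 + 7 = 14 days for Schedule C.

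| Day | Schedule B | Schedule C |
|---|---|---|
| 8 | on-day 8 | off-day 1 |
| 55 | on-day 13 | off-day 6 |
| 56 | on-day 14 | off-day 7 |
| 57 | off-day 1 | on-day 1 |
| 58 | off-day 2 | on-day 2 |
| 59 | off-day 3 | on-day 3 |

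At the nominal days, Schedule B has one usable steady-state profile (Day 8) and Schedule C has none.

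**What Day 57 measures in Schedule C.** Section 2.1.6 gives a terminal half-life of 5 to 7 h for the capsule, which is assumed here for the tablet. Seven drug-free days are 168 h, which is 168/7 = 24 to 168/5 = 33.6 half-lives. Nothing carries over, and the profile repeats Day 1. Section 2.1.6 also puts steady-state exposure on twice-daily dosing about 50% above a single dose, so this profile read as AUCss gives 1/1.5 = 67% of the true value. A one-compartment check gives 1 − 2^(−12/7) = 70% to 1 − 2^(−12/5) = 81%.

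**What the Day 57 window offers.** Schedule B is on drug on Days 55 and 56. In Schedule C the Day 58 morning dose is the third of the on-week, 24 h after the first. Its 12 h AUC is 1 − 2^(−36/7) = 97% to 1 − 2^(−36/5) = 99% of steady state. The Day 59 morning dose is the fifth, and its AUC is above 99% (1 − 2^(−60/7) = 99.7%).

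**Count.** Section 12.4.5 plans about 15 patients per arm, so the four arms have 4 × 15 × 2 = 120 profiles after Day 1.

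- Nominal days: Schedule C 15 × 2 = 30, plus Schedule B 15 × 1 = 15. Total 45 of 120 (37.5%).
- Day 57 visits all on the usable side of the window: Schedule C Day 8 remains, 15 of 120 (12.5%).
- Group 2's convention applied (a week of dosing runs to Day 8): Schedule C Day 8 and Schedule B Day 57 become usable. Schedule C Day 57 remains, 15 of 120 (12.5%).

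**The case against.** A reader might infer that Schedule C can give no steady-state profile and that the objective fails for it. The documents do not support that, for three reasons.

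1. **The window.** The 2 days either side of Day 57 already admit on-drug days for Schedule B and near-steady-state days for Schedule C. This stands, but nothing directs sites to the usable side, and the nominal day is wrong in both arms.
2. **The meaning of one week.** Section 4.1.2.2 has Group 2 take the first formulation until Day 8, and Table 6 footnote f profiles that day after the morning dose. Footnote o of Table 7 likewise presupposes a Day 8 dose. On that convention Schedule C Day 8 would be usable. The Group 8 text does not adopt it, and Schedule C Day 57 remains a first dose under either reading. If the convention and the favourable side of the window both applied, no profile would be lost, but the protocol states neither.
3. **The analysis method.** Mixed-effects modelling can predict steady state from the Day 1 profile and the dosing history. A pre-dose sample on a first off-day would also still act as a trough. Model-based estimates therefore remain possible. At the nominal days, however, Schedule C would have no observed steady-state peak or AUC over a dosing interval, so its estimates would be largely extrapolated from single-dose data.

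It would also go too far to say that Section 12.1.1 takes steady-state parameters from the wrong days, since it names no days. How records are coded for the model is a matter for the analysis plan.

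**Conclusion.** The sampling days in Table 7 footnote o and Section 7.2.2.3 do not fit the calendars in Section 4.1.2.5. About 45 of 120 planned post-Day-1 profiles are affected at the nominal days, and about 15 of 120 on either of the two favourable readings taken alone.

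This rests on Day 1 being the first on-day, about 15 patients per arm, both profiles planned for every patient, and capsule half-life and accumulation carrying over to the tablet. The off-day positions need only the first of these.

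Schedules A and D, Schedule B Day 8 and the primary safety objective are unaffected. Because the objective is secondary and summarised descriptively, this is a should-fix.

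**What to change.** Reconcile Table 7 footnote o and Section 7.2.2.3 with Section 4.1.2.5 by listing PK days per schedule rather than per dosing frequency, with no change to dosing:

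- **Schedule B:** keep Day 8, and direct the Day 57 profile to Day 55 or 56.
- **Schedule C:** move the Day 8 profile to Day 7, the last on-day under the calendar as written, and direct the Day 57 profile to Day 58 or 59.
- **Schedules A and D:** unchanged.

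In Section 12.1.1, state that steady-state parameters for Schedules B and C use only on-treatment profiles, with actual dosing records entered in the model.

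The cost is an amendment to the wording, one Schedule C visit moved by a day (Day 7 is not now a visit day), and a narrower Day 57 window in two arms. The later profiles stay within the existing window, and the number of samples does not change.

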#### 4.1.4 Safety Review Committee (SRC)

After at least the first 3 patients have been treated for 28 days with AZD2281 tablets within groups 3 onwards, the SRC will evaluate the safety, tolerability and any available pharmacokinetic data for AZD2281 and decide the next dose.

The SRC will consist of:

- Study Team Physician, who will chair the committee, or delegate
- International Principal Investigator or delegate and other Principal Investigators as required
- At least one other physician from the following:
  - Global Safety Physician or delegate
  - Medical Science Director or delegate
  - Senior physician from another project

In addition, the Study Pharmacokineticist, Study Statistician, Patient Safety Scientist and Study Delivery Leader will be invited as appropriate. Further internal or external experts may be consulted by the SRC as necessary. The Global Safety Physician or delegate should always be present at the SRC if there are safety issues for discussion.

The SRC will review and assess all available safety data together with available PK data to make a decision on the dose for the next cohort of subjects. Safety information from later cycles of therapy in addition to cycle 1 data may be considered to assess this relative comparison of toxicity. The decision may be to escalate no further, to give the intended escalation dose or a greater/smaller dose increment which may involve an additional dose escalation step. If 400 mg bid tablet dose is tolerable, higher doses could be considered by the SRC.

The decision of the SRC on the next dose will be taken in consensus between the physicians. If consensus cannot be reached then the International Principal Investigator, who has the ultimate responsibility for the safety of the subjects, will take the final decision on the next dose level or whether to stop the study. The Medical Science Director, who may need to consider other factors, will be involved in this decision. The decisions and decision-making of the SRC on the next dose level will be documented and provided to the International Principal Investigator and Pharmacist prior to the commencement of dosing in the next group.

For details on dose limiting toxicities refer to Section [6.2.4.3](#).

## 4.2 Rationale for study design, doses and control groups

This study is intended to establish the comparative bioavailability of AZD2281 Melt-Extrusion (tablet) formulation to AZD2281 Gelucire® 44/14 (capsule) formulation.

Due to the genotoxic nature of AZD2281, this comparative bioavailability study will be conducted in a cancer patient population. A placebo group has been excluded as this would be unethical and the study is non-comparator as there are no assessments of efficacy.

The doses of 50 mg, 100 mg and 400 mg of the current Gelucire® 44/14 (capsule) formulation have been selected as they span the potential Phase II doses (100 mg bid and 400 mg bid) plus a lower dose (50 mg) at a previously defined linear part of exposure/dose relationship. Melt-Extrusion (tablet) formulation doses for Cohorts 1 and 2 have been selected based on assumption that a 2-fold increase in exposure seen in preclinical studies in the dog will translate into a 2 fold increase in man. The Melt-Extrusion (tablet) formulation dose for Cohort 3 will be selected once the comparative bioavailability of the Melt-Extrusion (tablet) formulations in Cohorts 1 and 2 have been determined.

Following completion and review of the first 3 cohorts, 200 mg bid AZD2281 has been chosen as the Melt-extrusion (tablet) formulation dose for continuous treatment. This has been based on modelling of single dose plasma concentration data and subsequent prediction of the tablet dose required to give multiple dose AZD2281 exposure similar to that previously seen following the 400 mg bid Gelucire® 44/14 capsule dose. Additional patients will be recruited to provide reassurance on the safety and steady state exposure of the Melt-extrusion 200 mg bid dose.

Analysis of data from the on-going continuous supply expansion phase has shown that the 200 mg bid tablet dose does achieve exposures within the range of those seen following dosing at 400 mg bid AZD2281 with the capsule. A direct intra-subject comparison of steady state exposure has shown that although the gmean  $C_{ss\ max}$  achieved following these doses of the two formulations was very similar, the gmean  $AUC_{ss}$  was approximately 20% lower following the tablet dose. The 200 mg bid tablet dose was very well tolerated but seemed to demonstrate lower anti-tumour activity compared to the 400mg bid capsule dose.

The addition of patients to the Continued Supply Expansion Phase is primarily intended to:

- Provide data to validate the predictions of steady state exposures following administration of Melt-extrusion (tablet) formulation at 200 mg bid
- Provide single dose and steady state exposure data following administration of Melt-extrusion (tablet) formulation at doses above 200 mg bid
- Provide safety data for the Melt-extrusion (tablet) formulation when given over an extended treatment period. This will be achieved by treating patients with ovarian and breast tumours associated with germline mutations in the BRCA 1 or BRCA 2 genes. From previous studies, median time on treatment prior to progression

approached 6 months, suggesting that this population will be suitable for assessing the longer-term safety and tolerability of the tablet formulation compared to 400 mg bid capsule formulation.

## 5. STUDY SELECTION CRITERIA

Patient population should be selected without bias.

Investigator(s) must keep a record of patients who entered pre-trial screening but were never enrolled eg, patient screening log. Each patient must meet all of the inclusion criteria and none of the exclusion criteria for this study. Under no circumstances can there be exceptions to this rule.

### 5.1 Inclusion criteria

For inclusion in the study, patients must fulfil all of the following criteria.

1. Provision of fully informed consent prior to any study specific procedures;
2. Patients must be > 18 years of age;
3. Histologically confirmed malignant advanced solid tumour, which is refractory to standard therapies (except Group 8 patients who must not be platinum refractory) or for which no suitable effective standard therapy exists. If a diagnosis based on a histological sample is not available, a diagnosis based on cytology is allowed for those tumour entities in which this method is a generally accepted alternative;
4. Eastern Co-operative Oncology Group (ECOG) Performance status 0 – 1 (see [Appendix D](#));
5. Patients must have adequate organ and bone marrow function measured within 7 days prior to administration of study treatment as defined below:
  - Haemoglobin  $\geq$  10.0 g/dL and no blood transfusions in the 4 weeks prior to randomisation (Group 8 only)  $\geq$  9.0 g/dL (all other groups)
  - Absolute neutrophil count (ANC)  $\geq$   $1.5 \times 10^9/L$
  - No dysplastic features on peripheral blood smear (Group 8 only)
  - White blood cells (WBC)  $> 3 \times 10^9/L$
  - Platelet count  $\geq 100 \times 10^9/L$
  - Total bilirubin  $\leq 1.5 \times$  institutional upper limit of normal (ULN)

- Aspartate transaminase (AST [SGOT])/Alanine transaminase (ALT [SGPT])  $\leq 2.5$  x ULN unless liver metastases are present in which it must be  $\leq 5$ x ULN
  - Serum creatinine  $\leq 1.5$  x ULN;
6. Patients must have a life expectancy  $\geq 16$  weeks;
7. Female patients must have evidence of non-childbearing status: negative urine or serum pregnancy test within 7 days of study treatment for women of childbearing potential, or postmenopausal status.
- Postmenopausal is defined by any one of the following:
- natural menopause with last menses  $>1$  year ago;
  - radiation-induced oophorectomy with last menses  $>1$  year ago;
  - chemotherapy-induced menopause with  $>1$  year interval since last menses;
  - serum follicle stimulating hormone, luteinising hormone and plasma oestradiol levels in the post menopausal range for the institution;
  - or surgical sterilisation (bilateral oophorectomy or hysterectomy).
8. Patient is willing and able to comply with the protocol for the duration of the study including undergoing treatment and scheduled visits and examinations.

[figure not shown]
Inclusion criterion that applies to the additional gBRCA ovarian or breast cancer patients being assigned to Group 1, 6, 7 and 8 in the Continued Supply Expansion Phase:

9. Patients must have solid tumours originating from the ovary or breast with a confirmed genetic BRCA1/2 mutation (Group 8 gBRCA ovarian [including primary peritoneal and fallopian tube] cancer patients only). The mutation must be confirmed as a loss of function mutation ie, a known deleterious or suspected deleterious mutation, the exact sequence variant must be recorded on the CRF and a redacted copy of the genetic diagnosis available at site.
10. Patients must have at least one lesion, not previously irradiated, that can be accurately measured as  $\geq 10$  mm in the longest diameter with spiral computed tomography (CT) scan or as  $\geq 20$  mm with conventional techniques (conventional CT or MRI) and which is suitable for accurate repeated measurements.

